12.4.2. Study Phases for Concomitant Medication

Study Phase	Definition Note: All programming should use start and end dates where available, CMSTRF and CMENRF are only to be used where dates are unavailable to help determine the correct study phase.
Pre-Treatment	
 Conmed Start Date < Study Treatment First Dose Date Conmed End Date < Study Treatment First Dose Date CMSTRF = "BEFORE" Randomisation date is missing i.e. subject was not randomised
On-Treatment	
 Study Treatment First Dose Date ≤ Conmed Start Date ≤ Study Treatment Last Dose Date + 28 Study Treatment First Dose Date ≤ Conmed End Date ≤ Study Treatment Last Dose Date + 28 (Conmed Start Date ≤ Study Treatment Last Dose Date + 28) and (Conmed End Date ≥ Study Treatment First Dose Date) (Conmed Start Date ≤ Study Treatment Last Dose Date + 28) and (CMENRF = "DURING/AFTER" or CMENRF = "AFTER" or CMSTRF = "DURING") (CMSTRF = "BEFORE" or CMSTRF = "DURING" or CMENRF = "DURING/AFTER") and (Conmed End Date ≥ Study Treatment First Dose Date) (CMSTRF = "BEFORE" or CMSTRF = "DURING") and (CMENRF = "DURING/AFTER" or CMENRF = "AFTER") CMSTRF = "DURING" CMENRF = "DURING/AFTER"
Post-Treatment	
 Conmed Start Date > Study Treatment Last Dose Date + 28

Study Phase	Definition Note: All programming should use start and end dates where available, CMSTRF and CMENRF are only to be used where dates are unavailable to help determine the correct study phase.
	
 • Conmed End Date > Study Treatment Last Dose Date + 28 • CMENRF = "AFTER" • CMENRF = "DURING/AFTER"
All phases	
 • Conmed start date is missing and CMSTRF is missing and conmed end date is missing and CMENRF is missing

NOTES:

- The duration of a single concomitant medication can extend over multiple study phases
- Please refer to [Appendix 7: Reporting Standards for Missing Data](#) for handling of missing and partial dates for concomitant medication. Use the rules in this table if concomitant medication date is completely missing.

12.4.3. Treatment Emergent Flag for Adverse Events

Flag	Definition
Treatment Emergent	
If AE onset date is on or after treatment start date & on or before treatment stop date + 28 days.
 
Study Treatment Start Date ≤ AE Start Date ≤ Study Treatment Stop Date + 28 days

NOTES:

- If the study treatment stop date is missing then the AE will be considered to be On-Treatment.

12.5. Appendix 5: Data Display Standards & Handling Conventions

12.5.1. Reporting Process

Software	

 The currently supported versions of SAS software will be used. 	
Reporting Area	
HARP Server	: uk1salx00175
HARP Compound	: /arenv/arprod/gsk3772847/mid207972/
final_01: This is where the end of study analysis will take place.	
Analysis Datasets	

 Analysis datasets will be created according to CDISC standards 	
Generation of RTF Files	

 RTF files will be generated for all reporting efforts 	

12.5.2. Reporting Standards

General	

 The current GSK Integrated Data Standards Library (IDSL) will be applied for reporting, unless otherwise stated (IDSL Standards Location: https://spope.gsk.com/sites/IDSLLibrary/SitePages/Home.aspx): 
 4.03 to 4.23: General Principles 5.01 to 5.08: Principles Related to Data Listings 6.01 to 6.11: Principles Related to Summary Tables 7.01 to 7.13: Principles Related to Graphics Do not include subject level listings in the main body of the GSK Clinical Study Report. All subject level listings should be located in the modular appendices as ICH or non-ICH listings 	
Formats	

 GSK IDSL Statistical Principles (5.03 & 6.06.3) for decimal places (DP's) will be adopted for reporting of data based on the raw data collected, unless otherwise stated. Numeric data will be reported at the precision collected on the eCRF. The reported precision from non eCRF sources will follow the IDSL statistical principles but may be adjusted to a clinically interpretable number of DP's. 	
Planned and Actual Time	

 Reporting for tables, figures and formal statistical analyses: 
 Planned time relative to dosing will be used in figures, summaries, statistical analyses and calculation of any derived parameters, unless otherwise stated. The impact of any major deviation from the planned assessment times and/or scheduled visit days on the analyses and interpretation of the results will be assessed as appropriate. Reporting for Data Listings: 
 Planned and actual time relative to study drug dosing will be shown in listings (Refer to IDSL Statistical Principle 5.05.1). Unscheduled or unplanned readings will be presented within the subject's listings. 	
Unscheduled Visits	

 Unscheduled visits will only be included in summary tables as part of 'minimum/maximum post baseline' 	

and 'minimum/maximum change from baseline' summary. 
 • Unscheduled visits will not be included in figures. • All unscheduled visits will be included in listings. 	
Descriptive Summary Statistics	
Continuous Data	Refer to IDSL Statistical Principle 6.06.1
Categorical Data	N, n, frequency, %
Graphical Displays	

 • Refer to IDSL Statistical Principals 7.01 to 7.13. 	

12.6. Appendix 6: Derived and Transformed Data

12.6.1. General

Multiple Measurements at One Analysis Time Point

 • Mean of the measurements will be calculated and used in any derivation of summary statistics but if listed, all data will be presented. • If there are two values within a time window (as per Section 12.3.1) the value closest to the target day for that window will be used. If values are the same distance from the target, then the mean will be taken. • Participants having both High and Low values for Normal Ranges at any post-baseline visit for safety parameters will be counted in both the High and Low categories of “Any visit post-baseline” row of related summary tables. This will also be applicable to relevant Potential Clinical Importance summary tables.
Study Day

 • Calculated as the number of days from First Dose Date: 
 • Ref Date = Missing → Study Day = Missing • Ref Date < First Dose Date → Study Day = Ref Date – First Dose Date • Ref Date ≥ First Dose Date → Study Day = Ref Date – (First Dose Date) + 1

12.6.2. Study Population

Age
Date of birth will be set as 30-JUN-YYYY where YYYY is the year of birth taken from the CRF. For participants who attended a screening visit, age will be calculated at the screening visit date.
Body Mass Index (BMI)
$BMI = \text{Weight (kg)} / \text{Height(m)}^2$
Treatment Misallocations
To allocate treatment, the number of doses of GSK3772847 and Placebo that were given will be calculated, and the subject will be assigned to whichever treatment has the higher number. The only exception will be when both treatments were given equally, in which case the subject will be assigned their randomised treatment.
Extent of Exposure (Therapeutic Coverage)

 • IP is administered approximately every 4 weeks and each dose viewed as providing therapeutic coverage for 4 weeks (28 days). • Number of days of exposure to study drug will be calculated based on the formula: Duration of Exposure in Days = Study Treatment Last Dose Date – (Study Treatment First Dose Date) + 29 • The only exception to this will be when a participant dies in which case Duration of Exposure in Days = Death Date – (Study Treatment First Dose Date) + 1

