2.2. Study Objective(s) and Endpoint(s)

Objectives	Endpoints
Primary Objectives	Primary Endpoints
To evaluate the efficacy of 3 doses of GSK3772847 (administered every 4 weeks) compared with placebo in moderate to severe asthma participants with allergic fungal airway disease (AFAD) who are currently on Standard of Care (SoC)	
 Change from baseline (Week 0) in blood eosinophils over time Change from baseline (Week 0) in fractional exhaled nitric oxide (FeNO) over time
Secondary Objectives	Secondary Endpoints
To evaluate the serum pharmacokinetics (PK) of 3 doses of GSK3772847 (administered every 4 weeks) in moderate to severe asthma participants with AFAD	
 Serum concentrations of GSK3772847
To evaluate the pharmacodynamics (PD) of GSK3772847 in moderate to severe asthma participants with AFAD	
 Serum levels of free and total soluble suppressor of tumorigenicity 2 (sST2)
To evaluate the levels and specificity of any anti-drug antibodies formed following dosing with GSK3772847	
 Incidence and titres of serum anti- GSK3772847 antibodies
To evaluate the health status of moderate to severe asthma participants with AFAD currently on SoC, and who are treated with GSK3772847 compared with placebo-treated participants	
 Change from baseline (Week 0) in Asthma Control Questionnaire -5 (ACQ-5) absolute score at Weeks 2, 4, 8 and 12 Change from baseline (Week 0) in Asthma Quality of Life Questionnaire (AQLQ) total and domain scores at Weeks 2, 4, 8 and 12 Proportion of responders to ACQ-5. A responder to

Objectives	Endpoints
	
ACQ-5 will be defined as a subject who has a decrease from baseline in ACQ-5 score of 0.5 or more at Weeks 2, 4, 8 and 12.
 
 • Proportion of responders to AQLQ. A responder to AQLQ will be defined as a subject who has an increase from baseline in AQLQ score of 0.5 or more at Weeks 2, 4, 8 and 12.
To evaluate the effect on lung function of moderate to severe asthma participants with AFAD currently on SoC, treated with GSK3772847 compared with placebo	
 • Change from baseline (Week 0) in spirometry parameters over time including but not limited to pre-bronchodilator Forced expiratory volume in 1 second (FEV1).

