12.2. Appendix 2: Schedule of Activities

12.2.1. Protocol Defined Schedule of Events

Procedure	Screening (±5days)	Run-in (±5days)	Treatment Period (Visit window ±3days)				End of Treatment / EW (±3days)	FU (±3days)	Notes
			V3	V4	V5	V6			
Visit	V1	V2	V3	V4	V5	V6	V7	V8	
Week	-4	-2	0	2	4	8	12	24	
Day	-28	-14	1	15	29	57	85	169	
Informed consent	X								May be obtained prior to Screening.
Inclusion and exclusion criteria	X	X	X						Recheck clinical status before 1 st dose of study medication.
Demography	X								
Full physical examination	X								To include height and weight
Medical/medication/ drug/alcohol/smoking history	X								Including smoking history, substance abuse, medical conditions and family history of premature cardiovascular disease; asthma disease duration and exacerbation history
Human immunodeficiency virus (HIV), Hepatitis B and C screening	X								If test otherwise performed within 3 months prior to first dose of study treatment, testing at screening is not required
Genetics									
Informed consent for Pharmacogenetic blood sample		X							

Procedure	Screening (±5days)	Run-in (±5days)	Treatment Period (Visit window ±3days)				End of Treatment / EW (±3days)	FU (±3days)	Notes
			V3	V4	V5	V6			
Visit	V1	V2	V3	V4	V5	V6	V7	V8	
Week	-4	-2	0	2	4	8	12	24	
Pharmacogenetic (PGx) blood sample			X						PGx sample may be drawn any time from Visit 3 onwards, pre-dose. Informed consent must be obtained before collecting a sample.
Study Treatment and Questionnaires									
Randomisation			X						
Study treatment			X		X	X			
Dispense diary card		X							To be completed daily.
Diary card review			X	X	X	X	X		
Collect diary card							X		
Rescue medication dispensing		X	X ¹	X ¹	X ¹	X ¹			1. As needed
ACQ-5	X		X	X	X	X	X		Test to be performed before all other assessments
AQLQ			X	X	X	X	X		Test to be performed immediately after ACQ-5
Efficacy									
Haematology (including eosinophil count)	X		X ¹	X	X	X	X		1. Pre-dose
FeNO	X		X	X	X	X	X		Test to be performed pre-dose
Spirometry	X		X	X	X	X	X		Test to be performed pre-dose

Procedure	Screening (±5days)	Run-in (±5days)	Treatment Period (Visit window ±3days)				End of Treatment / EW (±3days)	FU (±3days)	Notes
			V3	V4	V5	V6			
Visit	V1	V2	V3	V4	V5	V6	V7	V8	
Week	-4	-2	0	2	4	8	12	24	

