12.10.5. Efficacy Tables

Efficacy: Tables					
No.	Population	IDSL / Example Shell	Title	Programming Notes	Deliverable [Priority]
Primary Efficacy: Blood Eosinophils and FeNO					
2.01.	mITT	EX1	Summary of Exposure to Study Treatment	ICH E3	SAC
2.02.	mITT		Summary of Raw and Change from Baseline in Blood Eosinophils		SAC
2.03.	mITT		Summary of Raw and Change from Baseline in FeNO		SAC
Secondary Efficacy: Spirometry					
2.04.	mITT		Summary of Raw and Change from Baseline in FEV ₁		SAC
Secondary Efficacy: Patient Reported Outcomes					
2.05.	mITT		Summary of Raw and Change from Baseline in ACQ-5 Total Score		SAC
2.06.	mITT		Summary of ACQ-5 Responders		SAC
2.07.	mITT		Summary of Raw and Change from Baseline in AQLQ Total Score		SAC
2.08.	mITT		Summary of AQLQ Responders		SAC

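### The exposure formulas in SAP 12.6.2 do not return the stated 28 days per dose: the death rule has no cap, and a skipped dose counts as covered

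*SAP*

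**What the plan says.** Section 12.6.2, under the exposure heading that carries the words therapeutic coverage in brackets, sets out a principle and two formulas.

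- Principle: "each dose viewed as providing therapeutic coverage for 4 weeks (28 days").
- Formula for participants who do not die: "Study Treatment Last Dose Date – (Study Treatment First Dose Date) + 29".
- Exception: "The only exception to this will be when a participant dies", in which case the duration is "Death Date – (Study Treatment First Dose Date) + 1".

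The first formula has no term for the number of doses given or for gaps between them. The exception covers any death, however long after the last dose.

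Section 12.6.1 sets the day-counting convention. From the first dose onward, study day is "Ref Date – (First Dose Date) + 1", so the first dose day is Day 1 and counts are inclusive. Section 12.10.5 lists the display that reports the result: Table 2.01, "Summary of Exposure to Study Treatment", for the mITT population.

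**The concern.** A derived variable should return what its definition says. Here the definition is 28 days of coverage per dose, and the formulas depart from it in three ways.

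1. A death after coverage has ended lengthens exposure. The evident purpose of a death rule is to shorten the count when coverage is cut off. Without a cap it does the reverse for a death in follow-up.
2. Only the first and last dose dates enter, so a participant who missed the middle dose gets the same duration as one who had the full course.
3. The constant 29 does not match 28 days on the SAP's inclusive count.

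At stake is the accuracy of a planned display. The wrong values would fall on participants who died or missed a dose. Section 2.1 says that 20 randomised subjects were not reached before termination, so one inflated value could visibly move a group mean or maximum in Table 2.01.

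**Working it through.** **Inputs**

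- Coverage per dose: 28 days (12.6.2).
- Planned dosing: three doses, four weeks apart (2.2: "To evaluate the efficacy of 3 doses of GSK3772847 (administered every 4 weeks").
- Planned days from the schedule in 12.2.1: "Day -28 -14 1 15 29 57 85 169". Study treatment is marked at Days 1, 29 and 57, end of treatment is Day 85 and follow-up is Day 169. These are nominal; the window is ±3 days.
- Inclusive day count (12.6.1).
- On-treatment period (12.4.1) and treatment-emergent window (12.4.3): both end at stop date + 28 days. I take the stop date to be the last dose date.

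**Formulas**, with F = first dose day, L = last dose day and D = death day:

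- SAP, no death: L − F + 29.
- SAP, death: D − F + 1.
- Coverage A, the stated 28 days: number of distinct days covered when each dose covers its dose day and the next 27, cut at death.
- Coverage B: the same, but each dose covers its dose day and the next 28 (29 calendar days). This is the reading most favourable to the constant 29.

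**Results (days)**

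| Scenario | SAP rule | Coverage A | Coverage B |
|---|---|---|---|
| 1 dose (Day 1) | 1 − 1 + 29 = 29 | 28 | 29 |
| 2 doses (Days 1, 29) | 29 − 1 + 29 = 57 | 56 | 57 |
| 3 doses (Days 1, 29, 57) | 57 − 1 + 29 = 85 | 84 | 85 |
| Middle dose skipped (Days 1, 57) | 57 − 1 + 29 = 85 | 56 | 58 |
| 3 doses, death Day 70 | 70 − 1 + 1 = 70 | 70 | 70 |
| 3 doses, death Day 150 | 150 − 1 + 1 = 150 | 84 | 85 |
| 1 dose, death Day 160 | 160 − 1 + 1 = 160 | 28 | 29 |
| 3 doses late but in window (Days 1, 32, 60) | 60 − 1 + 29 = 88 | 84 | 86 |

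**Reading the table**

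- *Death rule.* It is right when death falls within coverage (Day 70). After coverage ends it adds days. Death on Day 150 gives 150 against 85 for the same participant alive, an excess of 65 days. With the last dose on Day 57, section 12.4.1 puts the end of the on-treatment period at Day 57 + 28 = Day 85. The SAP therefore calls Days 86 to 150 post-treatment and still counts them as exposure.
- *Skipped dose.* The first dose covers Days 1 to 28, so Days 29 to 56 (28 days) are uncovered. The formula counts them and adds its extra day: 85 − 56 = 29 days too many, or 29/56 = 52%.
- *Constant.* On schedule, the excess over 28 days per dose is always one day: 29, 57 and 85 against 28, 56 and 84. For a full course that is 1/84 = 1.2%.
- *Does Coverage B rescue the rule?* It reproduces 29, 57 and 85 exactly. It does not reproduce the skipped dose (58 against 85) or the late death (85 against 150).

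**The case against.** The strongest reply concerns the constant. L − F + 29 is the inclusive count from first dose to last dose + 28 days, the same endpoints as the treatment-emergent window in 12.4.3, and for a full course it ends on Day 85, the scheduled end-of-treatment visit. It may be a deliberate convention of dose day plus 28 days. That stands, and it reduces this part to a one-day inconsistency of wording between 12.6.2 and 12.4.3.

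On the skipped dose, the quantity is labelled a duration, and a first-to-last span is a common simplification. Dosing is also described as only approximately every four weeks. This has some force against subtracting a few days for an in-window late visit. It does not explain counting a whole missed interval as covered when the section's heading and principle define exposure by coverage per dose.

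On the death rule, the likely intent was truncation, deaths are listed individually (Listings 17 and 48), and the SAP reports no late death. All true. The text still has no cap.

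Two stronger readings are tempting and fail. A reader might infer that the formula is wrong for everyone. It is not: participants who die use the + 1 rule and get no extra day within coverage, and for the others the extra day may be a convention. A reader might also infer that safety rates are distorted because exposure is their denominator. The SAP plans no exposure-adjusted rate. Categorical data are counts and percentages (12.5.2), adverse event Tables 3.01 to 3.04 are overviews and frequency summaries, and treatment emergence uses dates, not this duration.

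**Conclusion.** The point holds as an internal error in one derivation. In order of weight: the uncapped death rule, which returns 150 instead of 85 (or 84) days for a death on Day 150 after a full course and 160 instead of 29 (or 28) for a death on Day 160 after one dose; the span that hides a skipped dose, 85 instead of 56; and the one-day mismatch in the constant, which only needs reconciling.

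The figures assume nominal dose days and take the SAP's 28 days per dose as its intended definition. The first two parts survive if coverage is instead read as dose day plus 28.

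The impact is small. Results are descriptive, few participants were randomised, and the larger errors need a late death or a skipped dose, neither of which the SAP reports. Only Table 2.01, and any listing that shows the duration (Listing 12 may, but its shell is not shown), would change. No efficacy or safety estimate depends on it. The point concerns only how exposure is counted and implies nothing about dosing.

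**What to change.** Replace both formulas with one and delete the separate death formula:

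exposure = min(L + 27, D) − F + 1, where D applies only if the participant died.

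If the sponsor states that coverage runs to dose day + 28, in line with 12.4.3, use L + 28 instead. Either way, say which convention applies and use it throughout 12.6.2.

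Add one sentence: where a scheduled dose between the first and last doses was not given, subtract the days not covered by any dose. Tie this to a skipped dose, so that ordinary lateness within the visit window is not treated as a gap.

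Check on the cases above with + 27: full course, 84; death on Day 70, 70; death on Day 150, min(84, 150) − 1 + 1 = 84; one dose and death on Day 160, min(28, 160) − 1 + 1 = 28; doses on Days 1 and 57, 84 − 28 = 56; in-window late dosing (Days 1, 32, 60), 87 − 1 + 1 = 87 with nothing subtracted.

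The cost is one revised derivation. Intermediate dose dates are needed only where a dose was skipped, and the treatment misallocation rule in the same section already counts doses given. Reported exposure falls by one day for participants dosed on schedule (by none under the + 28 convention), and by more only after a skipped dose or a death beyond coverage.

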12.6.3. Safety

Maximum/Minimum On-Treatment Definitions for Vital Signs Data
Maximum and Minimum on-treatment: Maximum and Minimum on-treatment value over all time-points (including scheduled and unscheduled assessments) will be presented.

Adverse Events
Adverse Events of Special Interest (AESI)

Systemic Allergic/Hypersensitivity and Non-allergic Reactions:
 
 • Hypersensitivity (SMQ) [narrow] • Anaphylactic reaction (SMQ) [narrow] • Angioedema (SMQ) [narrow] 
Alterations in immune response (infections)
 
All infections and serious infections reported under the MedDRA system organ class of 'Infections and Infestations'. Specific events of interest are opportunistic infections with preferred terms matching identified/pre-determined terms based on a published list of pathogens and/or presentations of specific pathogens to be considered as opportunistic infections in the setting of biologic therapy [Winthrop et al, 2015].
 
Alterations in immune response (malignancies):
 
All neoplasms reported under the MedDRA system organ class of 'Neoplasms, benign, malignant and unspecified (including cysts and polyps)'. Specific events of interest are malignancies which will be identified through matching of collected preferred terms with those from the following:
 
Sub-SMQs under the Malignancies SMQ:
 
 • Malignant tumours sub-SMQ (narrow terms) • Tumours of unspecified malignancy sub-SMQ (narrow terms) 
Alterations in cardiovascular safety:
 
Cardiac disorders and serious cardiac disorders reported under the MedDRA system organ class of 'Cardiac Disorders'. Serious cardiac, vascular and thromboembolic (CVT) events, identified as all serious events classified under the MedDRA system organ classes of 'Cardiac Disorders' and of 'Vascular Disorders', and thromboembolic events identified through matching of collected preferred terms with those from the following:
 
Sub-SMQs under the Embolic and thrombotic events SMQ:
 
 • Embolic and thrombotic events, arterial sub-SMQ (narrow terms) • Embolic and thrombotic events, venous sub-SMQ (narrow terms) • Embolic and thrombotic events, vessel type unspecified and mixed arterial and venous sub-SMQ (narrow terms) 
Sub-SMQs under the Ischaemic Heart Disease SMQ
 
 • Myocardial infarction sub-SMQ (narrow terms) • Other Ischaemic heart disease sub-SMQ (narrow terms) 
Sub-SMQs under the Central Nervous System Vascular Disorders SMQ
 
 • Ischaemic central nervous system vascular conditions sub-SMQ (narrow terms) • Central nervous system vascular disorders, not specified as haemorrhagic or ischaemic sub-SMQ (narrow terms) • Serious ischemic adverse events, a subset of the serious CVT events identified through matching of collected preferred terms with those from the following: 
Local Injection Site Reactions
 
Local injection site reactions are identifying through preferred terms which had been selected by medical review of the MedDRA dictionary and are provided in a separate spreadsheet.

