8.2. Vital Signs, Electrocardiogram (ECG) and Holter

Summary statistics for vital signs at baseline, Weeks 0, 4, 8, 12, and 24 will be produced along with change from baseline summaries for each post baseline timepoint. In addition, the change between post-dose and pre-dose vital signs measurements will be summarised at weeks 0, 4 and 8.

A summary of ECG findings along with a table that shows the maximum increase in QTcF values post-baseline relative to baseline category will be produced.

In addition a summary of Holter interpretations will be produced for participants with at least 16 hours of data, however all data will be listed.

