12.4. Appendix 4: Study Phases and Treatment Emergent Adverse Events

12.4.1. Study Phases

Assessments and events will be classified according to the time of occurrence relative to study treatment start date.

Study Phase	Definition
Pre-Treatment	Date ≤ Study Treatment Start Date
On-Treatment	Study Treatment Start Date < Date ≤ Study Treatment Stop Date + 28 days
Post-Treatment	Date > Study Treatment Stop Date + 28 days

Completion of study epochs will be defined as the following:

Study Phase	Definition of Completion
Run-in	Randomised into study and received first dose of study treatment
Treatment	Completed Week 12 visit
Follow up	Completed 12 week follow-up period

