12.10.6. Safety Tables

Safety: Tables					
No.	Population	IDSL / Example Shell	Title	Programming Notes	Deliverable [Priority]
Adverse Events (AEs)					
3.01.	SAFF	SAFE_T01	Overview of On-treatment Adverse Events During the Study		SAC
3.02.	SAFF	AE1	Summary of All On-treatment Adverse Events by System Organ Class and Preferred Term	ICH E3	SAC
3.03.	SAFF	AE1	Summary of All On-treatment Serious Adverse Events by System Organ Class and Preferred Term	ICH E3	SAC
3.04.	SAFF	AE3	Summary of All On-treatment Adverse Events by Overall Frequency	ICH E3, summarise by PT	SAC
Laboratory: Chemistry					
3.05.	SAFF	LB1	Summary of Worst Case Chemistry Results Relative to Normal Range Post-Baseline Relative to Baseline	ICH E3	SAC
Laboratory: Hematology and Cardiac Markers					
3.06.	SAFF	LB1	Summary of Worst Case Hematology and Cardiac Markers Results Relative to Normal Range Post-Baseline Relative to Baseline	ICH E3	SAC

Safety: Tables					
No.	Population	IDSL / Example Shell	Title	Programming Notes	Deliverable [Priority]
ECG and Holter					
3.07.	SAFF	EG1	Summary of ECG Findings	IDSL	SAC
3.08.	SAFF	EG11	Summary of Maximum Increase in QTcF Values Post-Baseline Relative to Baseline by Category	IDSL	SAC
3.09.	SAFF	HM1	Summary of Holter Interpretations	IDSL	SAC
Vital Signs					
3.10.	SAFF	VS1	Summary of Vital Signs	ICH E3	SAC
3.11.	SAFF	VS1	Summary of Change from Baseline in Vital Signs	ICH E3	SAC
3.12.	SAFF	VS1	Summary of Change from Pre-dose to Post-dose in Vital Signs	ICH E3	SAC

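### The on-treatment maximum and minimum for vital signs cannot include any reading taken after the first infusion on Day 1, because SAP 12.4.1 classes the whole start date as Pre-Treatment

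*SAP*

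**What the plan says.** - **Definition of the extreme.** SAP 12.6.3, under a title that refers to on-treatment definitions for vital signs: "Maximum and Minimum on-treatment value over all time-points (including scheduled and unscheduled assessments) will be presented".
- **Study phases.** SAP 12.4.1 applies to assessments as well as events and uses calendar dates only. Pre-Treatment is "Date ≤ Study Treatment Start Date", On-Treatment is "Study Treatment Start Date < Date ≤ Study Treatment Stop Date + 28 days" and Post-Treatment is "Date > Study Treatment Stop Date + 28 days".
- **The same boundary elsewhere.** For concomitant medications (12.4.2) and treatment-emergent adverse events (12.4.3), the on-treatment period includes the first-dose date.
- **Unscheduled readings.** SAP 12.5.2: "Unscheduled visits will only be included in summary tables as part of 'minimum/maximum post baseline", or as part of the matching change-from-baseline summary. This is a general rule and does not name vital signs.
- **Planned displays.** SAP 8.2: "Summary statistics for vital signs at baseline, Weeks 0, 4, 8, 12, and 24 will be produced". It adds change from baseline, and the pre-dose to post-dose change at Weeks 0, 4 and 8. The displays are Tables 3.10, 3.11 and 3.12, the last titled "Summary of Change from Pre-dose to Post-dose in Vital Signs". All three use standard shell VS1, whose rows are not shown. Listing 32 gives all vital-sign data.

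**The concern.** A maximum or minimum that accepts unscheduled readings is there to catch the worst value after exposure, including one taken because a participant felt unwell during or after an infusion. The first infusion is the first time any participant meets the drug, and the phase rule assigns everything recorded on that date to the period before treatment.

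The result is inconsistent within the SAP. An adverse event starting on Day 1 is treatment-emergent under 12.4.3, but the blood pressure or heart rate measured during it is Pre-Treatment under 12.4.1. Under 5.2 baseline is the latest pre-dose value, so a Day 1 post-dose reading is post-baseline and Pre-Treatment at once. One programmer working from 12.6.3 with 12.4.1, and another working from the post-baseline wording in 12.5.2, would take the extreme over different readings. Vital signs are a named safety endpoint in 2.2, and because 12.5.2 limits unscheduled readings to minimum and maximum summaries, the by-visit rows cannot make up the loss for those readings.

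**Working it through.** The SAP gives no figure on this point, so the check is to classify each scheduled reading under its own rules.

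**Inputs**
- Visit days from 12.2.1: "Day -28 -14 1 15 29 57 85 169". Dosing is at Weeks 0, 4 and 8, that is Days 1, 29 and 57.
- Vital signs from 12.2.1: before and after dosing on each dosing day, and one reading each at Weeks 12 and 24. None is scheduled at Week 2.
- Start date = Day 1.
- Assumption: stop date = last dose date = Day 57. Section 12.4.1 speaks of a stop date and 12.4.2 of a last dose date, and the SAP does not equate them.

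**Rule.** Pre-Treatment if day ≤ 1; On-Treatment if 1 < day ≤ 57 + 28 = 85; Post-Treatment if day > 85.

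| Scheduled post-baseline reading | Day | Phase under 12.4.1 | In the extreme? |
|---|---|---|---|
| Week 0 post-dose | 1 | Pre-Treatment | No |
| Week 4 pre-dose | 29 | On-Treatment | Yes |
| Week 4 post-dose | 29 | On-Treatment | Yes |
| Week 8 pre-dose | 57 | On-Treatment | Yes |
| Week 8 post-dose | 57 | On-Treatment | Yes |
| Week 12 | 85 | On-Treatment, on the limit | Yes |
| Week 24 | 169 | Post-Treatment | No |

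**Results**
- On schedule, 2 of 7 readings are left out.
- Week 12 sits exactly on the limit (57 + 28 = 85). If it falls one day late relative to the last dose, it becomes Post-Treatment and 3 of 7 are left out. The visit window is ±3 days, so this can happen without a deviation.
- If the stop date were later than Day 57, Week 12 would have some margin. Week 24 would still be excluded unless the stop date were Day 169 − 28 = Day 141 or later. No choice of stop date brings back the Day 1 reading.
- With the start corrected and on-treatment kept, 6 of 7 readings count on schedule. With a post-baseline definition through Week 24, 7 of 7 count.

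**Which boundary was intended.** Sections 12.4.2 and 12.4.3 include the start date. Section 12.7.2.1 moves certain partial adverse-event dates to the treatment start date and then calls the event on-treatment under Appendix 4. That agrees with 12.4.3 and not with 12.4.1, so the strict inequality in 12.4.1 is the one out of line.

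**The case against.** The other side has several fair points.

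- **General against specific.** Section 12.5.2 is a convention on where unscheduled visits may appear, and 12.6.3 is the only definition specific to vital signs. Laboratory and QTcF tables using post-baseline does not oblige vital signs to follow. This stands: the difference in terms between 12.5.2 and 12.6.3 is loose wording. The firmer conflict is between 12.4.1 and 12.4.2/12.4.3.
- **Week 24.** It lies 169 − 57 = 112 days (16 weeks) after the last scheduled dose. Leaving it out fits the 28-day limit for adverse events and the 28-day coverage per dose in 12.6.2. This stands: it is a choice, not an error.
- **The readings are reported elsewhere.** A first-infusion effect shows directly in the Week 0 pre-dose to post-dose change, scheduled Week 0 and Week 24 readings are in the by-visit summaries, and Listing 32 holds everything. This stands for scheduled readings. It does not help an unscheduled Day 1 reading, which would reach the listing only.
- **Missing rows.** Neither 8.2 nor the titles of Tables 3.10 to 3.12 mention a maximum or minimum, so a reader might infer that the extreme is never produced. The documents do not support that, because shell VS1 may carry those rows. It is a point to confirm.
- **Size.** A reader might infer from the table above that about a third of true extremes are missed. The documents do not support that either. Equal likelihood across the 7 readings gives 2/7 = 29%; anything higher needs late Week 12 visits, stop date equal to last dose date, or an assumed first-infusion shift. The SAP gives no data on within-subject variation to support any such figure.

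**Conclusion.** The point holds for Day 1. As written, the rules remove the scheduled reading after the first infusion, and any unscheduled reading later that day, from the vital-sign maximum and minimum. This follows from the date rule alone, whatever the stop date is taken to be.

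The size is best given as a count: 2 of 7 scheduled post-baseline readings are outside the extreme on schedule, of which one (Day 1 post-dose) is wrongly excluded and one (Week 24) is a defensible exclusion. Week 12 may also drop out, if stop date means last dose date. No share of missed extremes and no bias in standard-deviation units can be derived from the documents.

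The practical effect is small. It touches the maximum and minimum only, in a study that is summarised descriptively and that, by Table 1 in 2.1, did not reach 20 randomised subjects. It is still worth correcting, because a stated rule drops a post-exposure safety reading and the remedy is close to free.

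**What to change.** 1. In 12.6.3, state that the maximum and minimum cover every scheduled and unscheduled reading taken after the start of the first infusion.
2. In 12.4.1, reconcile the start boundary with 12.4.3 so that Day 1 post-dose assessments are On-Treatment and Day 1 pre-dose assessments stay Pre-Treatment. Changing the inequality alone would pull the baseline reading into the on-treatment period, so use planned time relative to dosing for scheduled readings and clock time for unscheduled ones. Section 5.2 treats Day 1 assessments as pre-dose where time is not collected, so an untimed unscheduled reading would still count as pre-dose.
3. Use one term for the extreme in 12.5.2 and 12.6.3: either post-baseline through Week 24, or on-treatment with a footnote that readings after stop date + 28 days are excluded. If on-treatment is kept, say whether the stop date is the last dose date, since that decides whether a late Week 12 reading counts.
4. Confirm that Tables 3.10 and 3.11 (shell VS1) carry the maximum and minimum rows, and add them if not.

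The cost is a few lines of text, a small change to the phase derivation and at most two rows in each of two existing tables. No new data are needed. The post-baseline option mixes off-drug Week 24 values into the extreme, which a footnote can state.
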